7.6 Risks and benefits

The risk to subjects in this trial will be minimized by compliance with the eligibility criteria and study procedures, close clinical monitoring.

There are no therapy changes or innovations in this study. The drug therapy administration is carried out strictly in accordance with the approved instructions for medical use, only with the registered indications and in accordance with appropriate clinical practice.

The study is designed to establish for patients with T2DM and obesity the reduction of the body weight, improvement of glycemic and lipid metabolism, and reducing blood pressure level. We expect that the study can improve a QoL and reduce diseases complications in the study populations. Nvs survey on hypoglycemia will be used to assess the quality of life in patients (**Appendix 2**).

8 Population

The study is expected to include approximately 100 patients with T2DM and obesity. It is planned to have 100 patients in the active group who will be on active life style management; the control group will be 30 patients who will be matched with active group in terms of their indicators. Both groups will receive standard drug therapy for diabetes.

The control group should match the active group. The following criteria should be taken into account (criteria of inclusion and exclusion): match in BMI (<30; ≥30) and baseline HbA1c (<7.5; ≥7.5). The decision to include a patient into active or control group should be made by a doctor.

Drop-out of patients is expected for about 20% of patients compared with the originally included population. The drop-out criteria is three in a row missed group classes in the first 12 weeks of the study in active group.

The drop-out in control group is not expected.

Patients will be distributed among two participating research centers.

The study will be executed in two sites, the [REDACTED] in Moscow and the [REDACTED] in Kazan. The adult patients with T2DM (men and women at the age of more than 18 years) will be under the observation if they need in the active weight loss according to the physician's decision and if a doctor decides that the active approach is necessary.

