protocol). Adverse events (but not serious adverse events) occurring before starting study treatment but after signing the informed consent form will be recorded on the Medical History/Current Medical Conditions Case Report Form. Abnormal laboratory values or test results constitute adverse events only if they induce clinical signs or symptoms, are considered clinically significant or require therapy, and are recorded on the Adverse Events Case Report Form under the signs, symptoms or diagnosis associated with them.

As far as possible, each adverse event will also be described by:

1. the severity grade (mild, moderate, severe)
2. its relationship to the drug(s) of interest (suspected/not suspected)
3. its duration (start and end dates or if continuing at final exam)
4. whether it constitutes a serious adverse event (SAE)

Serious Adverse Events (SAEs)

Information about all serious adverse events will be collected and recorded on the Serious Adverse Event Report Form. To ensure patient safety each serious adverse event will also be reported to Novartis DS&E within 24 hours of the investigator learning of its occurrence.

An SAE is defined as an event which:

- Is fatal or life-threatening
- Results in persistent or significant disability/incapacity
- Constitutes a congenital anomaly/birth defect
- Requires inpatient hospitalization or prolongation of existing hospitalization, unless hospitalization is for:
 - Routine treatment or monitoring of the studied indication, not associated with any deterioration in condition (specify what this includes)
 - Elective or pre-planned treatment for a pre-existing condition that is unrelated to the indication under study and has not worsened since the start of the drug of interest
 - Social reasons and respite care in the absence of any deterioration in the patient's general condition
- Is medically significant, i.e., defined as an event that jeopardizes the patient or may require medical or surgical intervention to prevent one of the outcomes listed above e.g. may require treatment on an emergency outpatient basis for an event not fulfilling any of the definitions of a SAE given above and not resulting in hospital admission
- Transmission of infectious agent via medicinal product

No specific SAEs exempt from this reporting process are planned in this protocol.

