12.2 Safety assessment

The safety variables will be analyzed in the Safety Populations, missing measurements will not be imputed.

Adverse events

Adverse events will be coded using the Medical Dictionary for Regulatory Activities (MedDRA, version 19).

Data on adverse events will be presented in terms of the number and proportion of patients with any adverse events overall, by system organ class (SOC) and preferred term (PT).

The number (proportion) of patients with AE and the number of AE will be tabulated by system organ class and preferred term, as well as by relationship to study treatment and severity. Within each system organ class and preferred term, each patient will be counted only once with the closest relationship to the study treatment or maximum severity. In the case of missing value of severity or relationship, the AE will be considered in the table as "severe" and "related", respectively.

The following tables will be provided:

- The number (proportion) of patients with AE and the number of AEs by system organ class and preferred term;
- The number (proportion) of patients with AE and the number of AEs related to study treatment by system organ class and preferred term;
- Number (proportion) of patients with AE and the number of AEs by severity, by system organ class and preferred term;
- The number (proportion) of patients with AE and the number of AEs that led to discontinuation of the program (for the active group), by system organ class and preferred term;
- The number (proportion) of patients with AE and the number of AEs that are fatal, by system organ class and preferred term;
- The number (proportion) of patients with SAE and the number of SAE, by system organ class and preferred term;

The analysis will not include AEs that started before the start of a lifestyle change program for patients in the active group. In the case of a partial start date for AE, it will be compared as far as possible with the program start date to determine if it occurred prior to the start of the program. If the available information is not sufficient, the AE will be considered to have started after the beginning of the program.

The analysis of the SAE will include all registered SAE. Data on all AE / SAE will be presented in the form of listings.

Laboratory data

Laboratory investigations were conducted on Visit 1, Week 12 and 48 and included the following parameters:

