Biochemistry: total protein (g/l), cholesterol, LDL, HDL (mmol/L), triglycerides (mmol/L), ALT (U/l), AST (U/l), CPK (U/l), creatinine ($\mu\text{mol/L}$), GFR.

Haematology: hemoglobin (g/l), leukocytes ($10^9/l$) (+ formula), erythrocytes ($10^{12}/l$), platelets ($10^9/l$), ESR.

Urinalysis: color, transparency, relative density, protein, glucose, ketones.

Descriptive statistics will be used to analyze the laboratory data. Hematology and biochemistry lab parameters values and their absolute changes from baseline will be presented by groups and study visits. Tables of shifts relative to normal ranges (low / normal / high) will be tabulated by visit. For the urinalysis parameters, the number and proportion of the normal / non-clinically significant deviations / clinically significant deviations will be tabulated. All laboratory data will be presented in listings.

Vital signs

Systolic and diastolic pressure (mmHg), heart rate and respiratory rate will be recorded at each visit of the study. For the analysis of vital signs, descriptive statistics will be used. Parameters of blood pressure, heart rate and respiratory rate and their absolute changes in from baseline values will be tabulated by visit. All vital signs data will be presented in listings.

ECG

ECG was performed on Visit 1, Week 12 and 48. The ECG results (normal / non-clinically significant deviations / clinically significant deviations) will be tabulated as the number and percentage of patients with each of the assessments from the number of patients present at the visit.

Physical examination

The results of the physical examination, including an overall assessment of the basic parameters of the vital activity of the organism, will be recorded on Visit 1 and on all visits, beginning from Week 12 in both groups, and also 4 and 8 weeks after inclusion in the study for active group patients. The results of the physical examination will be tabulated as the number and percentage of patients with each of the assessments (normal / non-clinically significant deviations / clinically significant deviations) from the number of patients present at the visit.

13 Other variables

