The scale of individual perception of physical activity (the Borg scale) was filled on Visit 1 and at the end of the program in the active group. The score on the scale will be presented using descriptive statistics as the number and proportion of patients for each category. Changes will be presented as cross-tabulation of estimates at the beginning and after the program.

The questionnaire for hypoglycemia evaluation was filled on Visits 1, 24 and 48 weeks of observation. For each patient, the result for subscales 4, 5, 6, 7, 8, 9 will be calculated as the mean value of answers to subscale questions. The results for all subscales and changes from baseline will be presented descriptively by groups and visits.

14 Interim analysis

Not planned.

15 Presentation of results

Statistical analysis will be performed using IBM® SPSS® Statistics Version 19.0 or later. All results will be presented in the form of tables, listings and figures.

16 Changes in the statistical analysis plan

The analysis of the quantitative efficacy endpoints at each individual assessment visit using ANCOVA was replaced with an analysis based on a similar model, which takes into account the correlation between the repeated measurements, using the GEE method (Generalized Estimating Equations).

Secondary dichotomous endpoints - a decrease of HbA1c level by at least 0.5% from baseline, achievement of HbA1c $\leq 7\%$ by 12 months of observation, a decrease in SBP and DBP by at least 5 mmHg at 3, 6, 9, 12 months of observation - will also be analyzed using GEE (logistic regression of repeated changes) instead of logistic regression for individual evaluation visits.

17 References

1. ICH (1998). International Conference on Harmonization. Guideline E9 on Statistical Principles for Clinical Trials.

18 List of results

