Table 5.2.1 Frequency table for serious adverse events (Safety Population)

Table 6.1.1 Descriptive statistics for values of biochemistry analysis parameters and their changes by study visits (Safety Population)

Table 6.1.2 Shift tables for biochemistry analysis parameters by study visits (Safety Population)

Table 6.2.1 Descriptive statistics for values of hematology analysis parameters and their changes by study visits (Safety Population)

Table 6.2.2 Shift tables for hematology analysis parameters by study visits (Safety Population)

Table 6.3.1 Normal/abnormal assessment for the results of clinical urinalysis by study visits (Safety Population)

Table 7.1 Descriptive statistics for vital signs parameters values and their changes by study visits (Safety Population)

Table 8.1 Normal/abnormal assessment for ECG results by study visits (Safety Population)

Table 9.1 Normal/abnormal assessment for physical examination results by study visits (Safety Population)

Table 10.1 Questionnaire for hypoglycemia evaluation results (FAS)

Table 10.2 Individual perception of physical activity (Borg scale) results (FAS)

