18.2 List of Listing

- Listing 1.1 Disposition (All enrolled patients)
- Listing 1.2 Inclusion / exclusion criteria (All enrolled patients)
- Listing 1.3 Protocol deviations (All enrolled patients)
- Listing 1.4 Study visits (All enrolled patients)
- Listing 2.1 Demographic and other baseline characteristics (All enrolled patients)
- Listing 2.2 Medical history (All patients included)
- Listing 2.3 Clinical manifestations of diabetes (All enrolled patients)
- Listing 2.4 Concomitant complications (All enrolled patients)
- Listing 3.1 Concomitant hypoglycemic therapy (All enrolled patients)
- Listing 3.2 Concomitant therapy (All enrolled patients)
- Listing 3.3 Lifestyle program attendance (Safety Population, Active Group)
- Listing 4.1 Body weight and BMI dynamics (All enrolled patients)
- Listing 4.2 WC, HC, WHR dynamics (All enrolled patients)
- Listing 4.3 HbA1c and FBG dynamics (All enrolled patients)
- Listing 4.4 Vital signs dynamics (All enrolled patients)
- Listing 5.1 Adverse events (All patients included)
- Listing 5.2 Serious adverse events (All patients included)
- Listing 5.3 Adverse events leading to discontinuation (All enrolled patients)
- Listing 5.4 Fatal adverse events (All patients included)
- Listing 6.1 Biochemistry laboratory parameters dynamics (All enrolled patients)
- Listing 6.2 Hematology laboratory parameters dynamics (All enrolled patients)
- Listing 6.3 Clinical urinalysis parameters assessments dynamics (All enrolled patients)
- Listing 7 ECG results (All enrolled patients)
- Listing 8 Physical examination results (All enrolled patients)
- Listing 9.1 Questionnaire for hypoglycemia evaluation results (All enrolled patients)
- Listing 9.2 Individual perception of physical activity (Borg scale) results (All enrolled patients, active group)

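### ECG results are tabulated visit by visit without pairing to Visit 1, so Table 8.1 cannot show how many patients developed a new deviation

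*SAP*

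**What the plan says.** SAP 12.2 (ECG) has recordings at Visit 1, week 12 and week 48, each graded into one of three categories. The summary is described as: "The ECG results (normal / non-clinically significant deviations / clinically significant deviations) will be tabulated as the number and percentage of patients with each" assessment, with patients present at that visit as the denominator. Section 12.2 also states that missing safety measurements are not imputed. The only ECG table in SAP 18.1 is "Table 8.1 Normal/abnormal assessment for ECG results by study visits (Safety Population"). Individual readings appear in "Listing 7 ECG results (All enrolled patients") in SAP 18.2.

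Other measures in the same SAP are paired with their starting value. For haematology and biochemistry, section 12.2 says: "Tables of shifts relative to normal ranges (low / normal / high) will be tabulated by visit". For the Borg scale, section 13 says: "Changes will be presented as cross-tabulation of estimates at the beginning and after the program".

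There is a second route by which an ECG finding can be summarised. Protocol section 11 (Adverse events) says: "Abnormal laboratory values or test results constitute adverse events only if they induce clinical signs or symptoms, are considered clinically significant or require therapy". SAP 12.2 tabulates adverse events by system organ class and preferred term, and adds: "The analysis will not include AEs that started before the start of a lifestyle change program for patients in the active group".

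**The concern.** The basic question for a repeated safety test is how many patients without an abnormality at the start acquired one. Percentages by visit do not answer it. The week 48 percentage mixes persisting with new abnormalities. The change from Visit 1 mixes new abnormalities with resolved ones and with abnormal patients who are no longer seen. A flat percentage can mean that nothing happened, or that every abnormal reading at week 48 is new.

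This matters somewhat more here than in a trial where ECG is a formality. The intervention includes physical exercise, Protocol 10.4 names ECG as a safety assessment, and Protocol section 10 requires an ECG before exercise in patients at coronary risk. Protocol 8.1 provides for exercise limits where cardiovascular disease is present, so some abnormal readings at Visit 1 are plausible.

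The two groups may also start from different ECG profiles. The cardiologist's agreement (SAP 6.1) and the exclusion for inability to exercise (SAP 6.2) apply to the active group only, and the treating physician chooses the group. Drop-out is planned for in the active group alone. Unpaired percentages therefore compare poorly between groups as well as over time.

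**Working it through.** The plan states no ECG rate, so there is no figure to reproduce. The check asks what Table 8.1 would let a reader infer.

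**Inputs from the documents.** Active group 100 and control group 30 (Protocol 8, SAP 6). Protocol 8 on attrition: "Drop-out of patients is expected for about 20% of patients compared with the originally included population". That leaves 100 × (1 − 0.20) = 80 active patients at week 48. No control drop-out is expected, so 30 remain.

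**Assumed inputs.** The numbers of abnormal ECGs. The three categories are collapsed to abnormal or not; the arithmetic is the same whether abnormal means any deviation or a clinically significant one.

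**Formula.** Let Table 8.1 show a/N abnormal at Visit 1 and b/n at follow-up. Let k be the patients abnormal at Visit 1 who are still present, with max(0, a − (N − n)) ≤ k ≤ min(a, n). Let s of these be still abnormal, with 0 ≤ s ≤ k. Then

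- new abnormal = b − s, among n − k patients present who were not abnormal at Visit 1.

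The table gives a, N, b and n but neither k nor s. The lowest count takes s as large as possible. The highest count and rate take s = 0 and k = a (every abnormal patient stays and resolves).

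| Group | Visit 1 | Week 48 | Percentage shown | New cases possible | Highest rate |
|---|---|---|---|---|---|
| Active | 5/100 | 4/80 | 5.0%, 5.0% | 0 to 4 | 4/(80 − 5) = 4/75 = 5.3% |
| Active | 10/100 | 8/80 | 10.0%, 10.0% | 0 to 8 | 8/(80 − 10) = 8/70 = 11.4% |
| Active | 20/100 | 16/80 | 20.0%, 20.0% | 0 to 16 | 16/(80 − 20) = 16/60 = 26.7% |
| Control | 3/30 | 3/30 | 10.0%, 10.0% | 0 to 3 | 3/(30 − 3) = 3/27 = 11.1% |

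The control row shows that drop-out is not needed for the problem to arise.

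**Less extreme cases, starting from 10/100 in the active group.**

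- *Drop-out unrelated to ECG, some resolve.* Of the 10 abnormal patients 8 stay, and of the 90 others 72 stay. If 4 of the 8 resolve and 4 of the 72 become abnormal (4/72 = 5.6%), the table shows (8 − 4 + 4)/80 = 10.0%: no apparent change.
- *Drop-out related to ECG, none resolve.* If 6 of the 10 abnormal patients leave, 4 remain abnormal, and 90 − 14 = 76 others stay. With 4 new cases (4/76 = 5.3%) the table again shows (4 + 4)/80 = 10.0%.
- *Drop-out unrelated to ECG, none resolve.* With the same 4 new cases as in the first example, the table shows (8 + 4)/80 = 15.0%, and the increase is visible.

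So masking is possible but not certain, and the table cannot tell these cases apart.

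**The case against.** The strongest reply is that the part that matters clinically is already covered. A result judged clinically significant counts as an adverse event under Protocol section 11, and a pre-existing condition counts only if it worsens. The SAP then summarises these events by system organ class, preferred term, severity and relationship. This largely stands. What it leaves out is the change from normal to a non-clinically significant deviation. That generally does not meet the adverse event rule, although the SAP grades it, and no summary table shows it as new. Adverse event tables also depend on the finding being entered under a sign, symptom or diagnosis, and they do not use patients free of the finding at Visit 1 as the denominator. The reply that a shift table rests on investigator judgement too is fair: the categories are graded by the investigator. The shift table does, however, use a reading recorded for every ECG, with no separate decision to report an event.

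Second, the assumed rates may be too high for clinically significant readings in the active group, given the cardiologist's agreement and the exclusion for inability to exercise. This stands as a limit on size. The number of cases that can be hidden is at most the number abnormal at Visit 1, so few abnormal readings at the start leave little room. It bears less on minor deviations, which those rules do not screen out.

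Third, the SAP uses the same by-visit format for urinalysis and physical examination, the other graded items, and its shift tables are for numeric laboratory values. That is a consistent convention, but it does not make the format informative about change.

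Fourth, the listing holds about 130 × 3 = 390 readings that could be paired by hand. True: the information is poorly summarised, not lost.

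**Conclusion.** The concern holds and is minor. As planned, Table 8.1 cannot identify new ECG deviations, because it omits the link to Visit 1 and the Visit 1 status of those who leave. With unchanged percentages, the count of new cases may lie anywhere from zero to the full number abnormal at follow-up in every scenario tabulated: 0 to 8 in the active group at an assumed 10%, 0 to 16 at an assumed 20%, and 0 to 3 among controls at an assumed 10%.

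These figures rest on assumed ECG rates and on the planned group sizes and drop-out. The upper limits require every abnormal patient to stay and to resolve, so they are bounds and not expectations. The practical loss is greatest for non-clinically significant changes and for incidence among patients normal at Visit 1. No endpoint, hypothesis test or sample size is affected.

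**What to change.** Add to Table 8.1, or replace it with, a shift table by group for the Safety Population:

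- rows: Visit 1 category (normal, non-clinically significant, clinically significant);
- columns: the same three categories at week 12 and at week 48, each with a missing column for patients of that Visit 1 category who have no ECG at that visit.

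Below it, report as n/N for each follow-up visit:

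- newly occurring clinically significant deviations, among patients without one at Visit 1 who have an ECG at that visit;
- any new deviation, among patients normal at Visit 1 who have an ECG at that visit.

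The same layout could optionally be used for physical examination (Table 9.1) and urinalysis (Table 6.3.1).

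The cost is a sentence in SAP 12.2 and one table shell, adapted from the laboratory shift tables with the ECG categories and the missing column. No new data, visits or staff are needed.

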18.1 List of Tables

Table 1.1 Patient disposition (All patients)

Table 2.1 Demographic and other baseline characteristics (FAS)

Table 2.2.1 Medical history (FAS)

Table 2.2.1 Clinical manifestations of diabetes at the time of diagnosis (FAS)

Table 2.2.2 Clinical manifestations of diabetes at the time of inclusion (FAS)

Table 2.2.3 Concomitant complications (FAS)

Table 2.3 Concomitant hypoglycemic therapy of diabetes (FAS)

Table 2.4 Other concomitant therapy (FAS)

Table 3.1 Duration of treatment and participation in the program (Safety Population)

Table 3.2 Attended classes (Safety Population, Active Group)

Table 4.1.1 Descriptive statistics for body weight values and their changes in percent and absolute units for study visits (FAS)

Table 4.1.2 Decrease in body weight by at least 5% compared to baseline values for study visits (FAS)

Table 4.1.3.1 Analysis of the primary endpoint - decrease in body weight by at least 5% compared to baseline values at 12 months of observation (FAS)

Table 4.1.3.2 Sensitivity analysis for primary end point (PP)

Table 4.1.3.3 Sensitivity analysis for the primary endpoint using GEE (FAS)

Table 4.1.4. Analysis of the decrease in body weight by at least 5% compared to baseline values at 3, 6, 9 months of observation (FAS)

Table 4.1.5 Decrease in body weight by at least 10% compared with baseline values for study visits (FAS)

Table 4.1.6. Analysis of the decrease in body weight by at least 10% compared to baseline values at 3, 6, 9 and 12 months of observation (FAS)

Table 4.1.7 Analysis of absolute changes in body weight compared to baseline values at 3, 6, 9 and 12 months of observation (FAS)

Table 4.1.8 Analysis of changes in body weight in % compared with baseline values at 3, 6, 9 and 12 months of observation (FAS)

Table 4.2.1 Descriptive statistics for body mass index values and their changes in percent and absolute units by study visits (FAS)

Table 4.2.2 Analysis of changes in body mass index compared to baseline values at 3, 6, 9 and 12 months of observation (FAS)

Table 4.3.1 Descriptive statistics for waist circumference values and their changes by study visits (FAS)

Table 4.3.2 Analysis of changes in WC compared to baseline values (FAS)

Table 4.3.3 Descriptive statistics for the values of the hip circumference and their changes by study visits (FAS)

Table 4.3.4 Descriptive statistics for the values of WHR ratio and their changes by study visits (FAS)

Table 4.3.5 Analysis of changes in WHR compared to baseline values (FAS)

Table 4.4.1 Descriptive statistics for HbA1c values and their changes in percent and absolute units by study visits (FAS)

Table 4.4.2 Analysis of absolute changes of HbA1c compared to baseline values at 3, 6, 9 and 12 months of observation (FAS)

Table 4.4.3 Analysis of changes in HbA1c in % compared to baseline values at 3, 6, 9 and 12 months of observation (FAS)

Table 4.4.4. Reduction of HbA1c level by at least 0.5% of baseline by study visits (FAS)

Table 4.4.5 Analysis of the reduction in HbA1c level by at least 0.5% from baseline (FAS)

Table 4.4.6 Analysis of the achievement of HbA1c \leq 7% at 12 months of observation (FAS)

Table 4.4.7 Descriptive statistics for FBG values and their changes in percent and absolute units by study visits (FAS)

Table 4.4.8 Analysis of the absolute changes in FBG compared to the baseline values at 3, 6, 9 and 12 months of observation (FAS)

Table 4.4.9 Analysis of FBG changes in % compared to baseline values at 3, 6, 9 and 12 months of observation (FAS)

Table 4.5.1 - 4.5.2 Descriptive statistics for values of SBP and DBP and their changes in absolute units by study visits (FAS)

Table 4.5.3 - 4.5.4 Analysis of absolute changes in SBP and DBP compared to baseline values at 3, 6, 9 and 12 months of observation (FAS)

Table 4.5.6 - 4.5.8 Decrease in SBP and DBP by at least 5 mmHg from baseline (FAS)

Table 4.5.9 - 4.5.10 Analysis of the decrease in SBP and DBP by at least 5 mmHg from baseline by study visits (FAS)

Table 4.6.1 - 4.6.4 Descriptive statistics for lipid profile values (cholesterol, triglycerides, LDL, HDL) and their changes in percent and absolute units for study visits (FAS)

Table 4.7.1 - 4.7.4 Analysis of changes in % of lipid profile (cholesterol, triglycerides, LDL, HDL) compared to baseline values at 3 and 12 months of observation (FAS)

Table 4.8.1 - 4.8.4 Analysis of absolute changes in lipid profile (cholesterol, triglycerides, LDL, HDL) compared to baseline values at 3 and 12 months of observation (FAS)

Table 5.1.1 Frequency table for adverse events (Safety Population)

Table 5.1.2 Frequency table for adverse events by severity (Safety Population)

Table 5.1.3 Frequency table for adverse events by relationship to study treatment (Safety Population)

Table 5.1.4 Frequency table for adverse events leading to discontinuation (Safety Population)

Table 5.1.5 Frequency table for fatal adverse events (Safety Population)

Table 5.2.1 Frequency table for serious adverse events (Safety Population)

Table 6.1.1 Descriptive statistics for values of biochemistry analysis parameters and their changes by study visits (Safety Population)

Table 6.1.2 Shift tables for biochemistry analysis parameters by study visits (Safety Population)

Table 6.2.1 Descriptive statistics for values of hematology analysis parameters and their changes by study visits (Safety Population)

Table 6.2.2 Shift tables for hematology analysis parameters by study visits (Safety Population)

Table 6.3.1 Normal/abnormal assessment for the results of clinical urinalysis by study visits (Safety Population)

Table 7.1 Descriptive statistics for vital signs parameters values and their changes by study visits (Safety Population)

Table 8.1 Normal/abnormal assessment for ECG results by study visits (Safety Population)

Table 9.1 Normal/abnormal assessment for physical examination results by study visits (Safety Population)

Table 10.1 Questionnaire for hypoglycemia evaluation results (FAS)

Table 10.2 Individual perception of physical activity (Borg scale) results (FAS)

